8.2 Background Characteristics

Background characteristics will be analyzed for the total subjects in the Ivacaftor Arm.

8.2.1 Subject Disposition

Ivacaftor Arm:

The number of subjects in the following categories will be summarized:

- Enrolled (All Subjects Set)
- Enrolled and Dosed (Safety Set)
- Enrolled and having at least 1 post baseline efficacy assessment (FAS)
- Completed treatment
- Prematurely discontinued treatment and the reason for discontinuation
- Completed study
- Prematurely discontinued study and the reason for discontinuation
- Last treatment visit completed (Day 1, Week 2, Week 4, Week 8, Week 12, Week 18, Week 24, Week 36, Week 48, Week 60, Week 72, Week 84, Week 96)

A listing will be provided for subjects who discontinued treatment or who discontinued study with reasons for discontinuation.

8.2.2 Demographics and Baseline Characteristics

Demographics, medical history, and baseline characteristics will be summarized based on the Safety Set. For rollover subjects, the demographics and baseline characteristics from the Study 124 will be used.

Demographic data will include the following:

- Age (in months)
- Sex (female and male)
- Ethnicity (Hispanic or Latino, not Hispanic or Latino, and not collected per local regulations)
- Race (White, Black or African American, Asian, American Indian or Alaska Native, Native Hawaiian or Other Pacific Islander, not collected per local regulations, and Other)

Baseline characteristics will include the following:

- Weight (kg)
- Length (cm)
- Weight-for-length
- BMI (kg/m²)
- Weight-for-age z-score
- Length-for-age z-score
- Weight-for-length z-score

Disease characteristics will include the following:

- Age at CF diagnosis
- Maternal/pregnancy history: complications in pregnancy, gestational age at delivery, method of delivery
- Number of CF-related hospitalizations from birth to screening
- Number of pulmonary exacerbations requiring antibiotics that occurred from birth to screening
- Number of pulmonary exacerbations requiring IV antibiotics that occurred from birth to screening
- Does subject have abnormal liver function tests (LFTs) documented since birth?
- Any use (yes or no) of the following medications from birth to screening will be assessed: inhaled tobramycin, inhaled aztreonam, inhaled colimycin, inhaled hypertonic saline, dornase alfa, ibuprofen, azithromycin, and pancreatic enzyme replacement therapy.
- Historical pancreatic test measurements

8.2.3 Prior and Concomitant Medications

Medications will be coded using the World Health Organization-Drug Dictionary Enhanced (WHO-DDE).

Medications used in the study will be identified as prior, concomitant, or both according to the rules given below.

Medications used in the study will be classified as follows:

- **Prior medication:** any medication that started before the first dose of ivacaftor in the current study, regardless of when it ended
- **Concomitant medication:** medication received at or after dosing of ivacaftor in the current study, or medication that was received before dosing with ivacaftor in the current study and continued after dosing of ivacaftor
- **Post-treatment medication:** medication continued or newly received after the TE period.

If medication start date is on or after the date of the first dosing of ivacaftor in the current study, the medication will be summarized as concomitant medication regardless of whether the medication end date is missing or not. If the medication end date is before the date of the first dosing of ivacaftor in the current study, then the medication will be summarized as prior medication regardless of whether the medication start date is missing or not. If medication started before the first dosing of ivacaftor in the current study and continued after dosing of ivacaftor, the medication will be summarized as prior medication and separately as concomitant medication.

Prior medications and concomitant medications will be summarized descriptively using frequency tables by Preferred Name.

Both prior and concomitant medications will be based on the Safety Set, with concomitant medications provided for the final analysis.

Post-treatment medications will be provided in data listings only.

Details for imputing missing or partial start and/or stop dates of medication are described in Appendix C.

Note that for rollover subjects from Study 124 Part B or Part A/B, only medications entered in the current study will be summarized.

8.2.4 Study Drug Exposure

Duration of study drug exposure (in days) will be calculated as: last dose date – first dose date + 1 day, regardless of study drug interruption.

Exposure summaries will be based on the Safety Set.

8.2.5 Study Drug Compliance

Study drug compliance based on the number of sachets taken will be calculated as:
 $100 \times [(total\ number\ of\ sachets\ dispensed) - (total\ number\ of\ sachets\ returned)] / (total\ number\ of\ sachets\ planned\ to\ be\ taken\ per\ day \times duration\ of\ study\ drug\ exposure\ in\ days\ in\ the\ current\ study)$. The maximum percentage of sachets taken will be 100%.

Study drug compliance based on study drug exposure will be calculated as: $100 \times [1 - (\text{total number of days of any study drug interruption}) / (\text{duration of study drug exposure in days})]$.

Study drug compliance will be summarized descriptively by the number of subjects (n), mean, SD, median, min, and max. They will also be summarized in categories: <80% and $\geq 80\%$ using frequency tables.

Study drug compliance summaries will be based on the FAS.

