### **9.1.1.5 Ivacaftor Arm Early Termination of Treatment (All Subjects)**

Subjects who prematurely discontinue treatment before their last scheduled dose will be required to complete the ETT Visit, Safety Follow-up Visit, and Follow-up OE. The ETT Visit must be completed as soon as possible after the last dose of ivacaftor. If the ETT Visit occurs 3 weeks or later after the last dose of ivacaftor, the Safety Follow-up Visit will not be required.

Subjects who receive commercially available ivacaftor will be discontinued from ivacaftor dosing and will complete the ETT Visit and Follow-up OE; the Safety Follow-up Visit will not be required.

If the subject withdraws consent for the study, no further evaluations should be performed and no additional data should be collected. Vertex may retain and continue to use any data collected before such withdrawal of consent.

ETT assessments are listed in [Table 3-1](#) and [Table 3-2](#) for subjects from Study 124 Part B and [Table 3-3](#) for subjects not from Study 124 Part B.

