### **12.3.2.4 Study Drug Exposure and Compliance (Ivacaftor Arm Only)**

Exposure to ivacaftor (i.e., duration of treatment) will be summarized for the Safety Set in terms of duration of treatment a subject received (in days).

Dosing compliance will be summarized for the Safety Set and is calculated as the actual number of dosing occasions at which ivacaftor was administered as a percentage of the planned number of dosing occasions.

Duration of treatment and dosing compliance will be summarized by means of descriptive summary statistics.

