7.1.2 Full Analysis Set

The Full Analysis Set (FAS) will be defined as all subjects who are enrolled and receive at least 1 postbaseline efficacy assessment in the current study. The FAS will be used for all efficacy analyses, unless specified otherwise.

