7.1.3 Safety Set

The Safety Set will be defined as all subjects who receive at least 1 dose of study drug in the current study. The Safety Set will be used for all safety analyses, unless specified otherwise.

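### SAP 8.2.5 moves the compliance summary from the Safety Set to the FAS and changes its definition, and SAP 2.1 does not declare this

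*SAP*

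**What the plan says.** Protocol 12.3.2.4 fixes both the population and the measure: "Dosing compliance will be summarized for the Safety Set and is calculated as the actual number of dosing occasions at which ivacaftor was administered", expressed as a percentage of the occasions planned. It mentions no upper limit.

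SAP 8.2.5 differs in three ways.

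- **Population.** "Study drug compliance summaries will be based on the FAS". SAP 7.1.2 defines the FAS as "all subjects who are enrolled and receive at least 1 postbaseline efficacy assessment in the current study". SAP 7.1.3 defines the Safety Set as "all subjects who receive at least 1 dose of study drug in the current study".
- **Measure.** Two ratios replace the protocol's one. The first is sachets dispensed minus sachets returned, over sachets planned per day times days of exposure. The second is one minus interruption days over days of exposure.
- **Cap.** For the sachet ratio, "The maximum percentage of sachets taken will be 100" per cent. Results are also tabulated in two classes, below 80% and 80% or more.

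The section immediately before, SAP 8.2.4, keeps the protocol's population: "Exposure summaries will be based on the Safety Set".

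SAP 2.1 lists the changes from the protocol: the growth reference, ECG visits, the follow-up eye examination, dose determination at Week 96, the name of one z-score, and the pooling of subject sources. Compliance is not on the list.

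**The concern.** Compliance tells the reader of a safety study how much of the planned drug the children received. It should describe the same children as the exposure and safety tables. Here exposure duration is the denominator of both compliance ratios, yet exposure is summarised on one set and compliance on another. Membership of the FAS depends on having an efficacy measurement, which has no bearing on whether compliance can be computed. The natural condition is having been dosed, and that defines the Safety Set.

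The cap matters because it works in one direction only. Low values are shown in full and have their own class, while high values are set to 100% and merge with perfect compliance.

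None of the three changes is declared. SAP 2.1 goes down to the name of a z-score, so a reader would reasonably take its silence to mean that compliance follows the protocol.

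**Working it through.** There is no stated figure to reproduce, because the study is unpowered and descriptive. The check is a comparison of texts followed by two illustrations.

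**Step 1: the two texts side by side.**

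| Item | Protocol 12.3.2.4 | SAP 8.2.5 | Declared in SAP 2.1? |
|---|---|---|---|
| Population | Safety Set | FAS | No |
| Measure | Occasions given / occasions planned | Sachet ratio and interruption-day ratio | No |
| Upper limit | Not mentioned | 100% on the sachet ratio | No |

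The first two rows are conflicts. The third is an addition, since the protocol is silent on it.

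**Step 2: who is in the Safety Set but not the FAS.** Only a dosed subject with no postbaseline efficacy assessment.

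- Length and weight are efficacy variables. After Day 1 they are first scheduled at Week 2 for subjects not from Study 124 Part B and at Week 12 for rollover subjects (Protocol Tables 3-1 to 3-3).
- They are also scheduled at the Early Termination of Treatment (ETT) Visit and the Safety Follow-up Visit. Protocol 9.1.1.5 states: "Subjects who prematurely discontinue treatment before their last scheduled dose will be required to complete the ETT Visit, Safety Follow-up Visit, and Follow-up OE".
- SAP 8.1 windows ETT results like those of regular visits, unless the ETT Visit falls 21 days or more after the last dose, when it counts as safety follow-up. The rollover Week 12 growth window is Days 2 to 126 (SAP Appendix B). A rollover child who stops at Week 3 and promptly attends the ETT Visit is therefore in the FAS.
- A child can still be lost if consent is withdrawn early, because Protocol 9.1.1.5 then allows no further evaluations.

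**Step 3: size of the population change.** Let k be the number of dosed subjects outside the FAS, with 75 dosed. The documents do not give k. I assume a range of 1 to 8, a mean of 50% in those subjects and a mean of 95% in the rest. The FAS mean is then 95% throughout.

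- Share omitted: k/75, which is 1/75 = 1.3% to 8/75 = 10.7%.
- Safety Set mean for k = 1: (74 × 95 + 1 × 50)/75 = 94.4%.
- Safety Set mean for k = 8: (67 × 95 + 8 × 50)/75 = 90.2%.
- For k = 0, if every FAS subject was dosed, the two sets give the same result.

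**Step 4: effect of the cap.** Assume one sachet per 12-hourly dose, so 2 per day, for 672 days (the Week 96 target day in SAP Appendix B). Planned sachets are 2 × 672 = 1344.

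| Extra sachets unaccounted for | Uncapped ratio | Reported |
|---|---|---|
| 67 | 1411/1344 = 105% | 100% |
| 134 | 1478/1344 = 110% | 100% |
| 336 | 1680/1344 = 125% | 100% |
| 672 | 2016/1344 = 150% | 100% |

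The interruption measure is 100 × [1 − interruption days/exposure days]. Interruption days cannot be negative, so it cannot exceed 100% either. All these cases fall in the class of 80% or more.

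**The case against.** Two stronger readings are tempting, and the documents do not support either.

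**A reader might infer that children who stop early are excluded from the compliance summary.** They are not excluded as a group. The ETT Visit is required and includes a weight, so most early stoppers should qualify for the FAS. Only dosed subjects with no postbaseline efficacy assessment at all are lost, and there may be none.

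**A reader might infer that over-administration cannot show anywhere in the study.** That is true of the two compliance summaries but not of the SAP as a whole. SAP 8.2.6 names incorrect doses as a potential important protocol deviation, and SAP 8.1 provides individual listings for enrolled subjects. This route is weaker than a table, since deviations depend on study-team categorisation and are only listed, but it exists.

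Three further objections have force.

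- The cap does not contradict the protocol, which says nothing about truncation.
- Sachet counting has a basis in Protocol 10.6, which assesses accountability from returned dosage units. The data source is therefore not new; the formula is.
- A sachet ratio above 100% does not measure over-exposure, because lost or unreturned sachets raise it in the same way. It can also miss real excess. With 28 days at double use and 28 days missed, (616 × 2 + 28 × 4)/1344 = 100%. The protocol's own measure counts occasions, so it would not register extra drug given at one occasion either.

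What remains is the conflict over the population, the undeclared change of measure, and truncation in one direction only.

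**Conclusion.** The point holds as a documentation and consistency fault with a small possible effect. The protocol and SAP conflict on the analysis set for compliance and on how it is calculated. The SAP adds a cap, and SAP 2.1 declares none of the three.

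The population change omits 1.3% of about 75 dosed subjects for each child without a postbaseline efficacy assessment. How many there are is not in the documents and may be zero. The movement in the mean from 95% to between 94.4% and 90.2% rests wholly on the assumed k and compliance levels, so it shows scale and is not an estimate. The cap result rests on assuming one sachet per dose, but its direction does not: every uncapped value above 100% is reported as 100%.

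Exposure duration is still summarised for every dosed subject. All analyses are descriptive, and no endpoint analysis takes compliance as an input. This is worth correcting because the correction is cheap, not because a conclusion depends on it.

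**What to change.** 1. In SAP 8.2.5, summarise compliance on the Safety Set, as Protocol 12.3.2.4 requires and SAP 8.2.4 already does for exposure.
2. In SAP 2.1, record that the sachet ratio and the interruption-day ratio replace dosing occasions given over planned, and that the sachet ratio is capped at 100%.
3. Add one table row with the number of subjects whose uncapped sachet ratio exceeds 100%, and a footnote that such values may reflect lost or unreturned sachets.

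The cost is a few lines of SAP text and one table row. The small downside is that some values above 100% will be accounting artefacts, which the footnote covers. The first two items are the main correction and the third is a secondary improvement. If the database is already locked, the change can be documented in the clinical study report, as SAP section 3 provides.

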8.2.6 Important Protocol Deviations

Important protocol deviations (IPD) are a subset of protocol deviations that may significantly impact the completeness, accuracy, and/or reliability of the study data or that may significantly affect a subject's rights, safety, or well-being

IPD rules will be developed and finalized before database lock.

The protocol deviations that may be considered as potential IPDs include, but are not limited to:

- Violation of subjects' rights, safety or well-being
- Subject entered the study despite violation of any inclusion or exclusion criteria
- Subject was less than 80% compliant with study medications
- Subject received excluded concomitant medications
- Subject received the wrong treatment or incorrect doses
- Subject remained in study despite meeting withdrawal criteria

Occurrence of any of these events may be considered as potential IPDs, but the study team will categorize them as IPDs if they have the potential to affect interpretation of study results or a subject's rights, safety, or well-being. .

IPDs will be presented as an individual subject data listing only.

8.2.7 COVID-19 Impacted Visits

A listing containing subjects' visits impacted due to COVID-19 will be provided.

8.3 Efficacy Analysis

Statistical methodology will be restricted to descriptive statistics only. Unless specified otherwise, all efficacy analyses described in this section will be based on the FAS, for the Ivacaftor Arm overall.

The analysis will include all available measurements per the visit windowing rules described in [Appendix B](#).

8.3.1 Analysis of Primary Efficacy Variable

Not applicable.

8.3.2 Analysis of Secondary Efficacy/Pharmacodynamic Variable

The sweat chloride test is a standard diagnostic tool for CF, serving as a biomarker of CFTR activity.

Sweat chloride will be collected at visits as indicated in Appendix A. Absolute change from baseline in sweat chloride will be calculated as: $mean(SW_{Left}, SW_{Right}) - SW_{Base}$, where SW_{Left} and SW_{Right} are the measurements obtained on the left and right arms, respectively, at a particular visit and SW_{base} is the mean of right and left baseline measurements at baseline. If 1 of the 2 measurements at a time point is missing, the other will be used as the mean.

Note: A volume of ≥ 15 μL is required for an accurate determination of sweat chloride. Any results reported having volume < 15 μL will not be included in analysis. In addition, sweat chloride with concentration > 160 mmol/L will not be included in analysis.

Definition of Baseline: Only results obtained from sample collections completed prior to the first administration of study drug (in Study 124 for Study 124 baseline, and in Study 126 for Study 126 baseline) will be considered as baseline results. If sweat chloride collection was completed for 1 arm prior to the first dose and completed for the other arm after the first dose, the baseline will consist of a single measurement. If both sweat collections were completed after the first dose, the baseline sweat chloride result will be considered missing for analysis purposes.

If sweat chloride was not performed at baseline or if the volume of sweat obtained from both arms was insufficient for analysis (< 15 μL), or if the concentration of sweat chloride from both arms was > 160 mmol/L, the most recent historical sweat chloride result may be used to impute the missing baseline value.

Sweat chloride results (including changes from baseline) will be analyzed as a continuous variable using descriptive summary statistics by visit.

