Study drug administration s		X		X	X	X	X	X	X			

a Samples will be analyzed for fecal elastase-1 and other markers of intestinal inflammation, including fecal calprotectin. Samples may be collected (e.g., at home) up to 24 hours before the study visit (e.g., at home) and brought to the clinic. If the sample is collected in the clinic, the sample may be collected pre- or postdose.

o The fecal sample may be collected at any time during screening.

p At Screening, a sweat chloride test must be performed if the sweat chloride value is not available in the subject’s medical records and the value is needed to establish eligibility. For subjects with sweat chloride values documented in their medical records and for whom it is not needed to establish eligibility, the sweat chloride test at screening is not required. For all subjects, except those that completed a baseline sweat chloride test at screening, a Day 1 sweat chloride test will be performed predose. At all other visits up to the Week 24 Visit, the test must be performed within a window of ± 2 hours relative to the ivacaftor dose. After the Week 24 Visit, the sweat chloride test may be performed at any time during the visit.

q MBW will be performed on subjects for whom additional or separate informed consent was obtained for the procedures, and only at sites that are adequately trained and qualified to perform this assessment (Section 11.5.6). The Day 1 MBW must be performed within 1 week before the first dose, not postdose. The Week 96 MBW must be performed within 1 week before the last dose, not after the last dose. Detailed procedures will be supplied in a separate study manual.

r MBW will be performed at the Week 48 and Week 72 Visits (± 7 days).

s The morning dose of study drug will be administered at the Day 1, and 2-, 4-, 8-, 12-, 18-, and 24-Week Clinic Visits. After the Week 24 Visit, the morning dose need not be administered at the Clinic Visit. Additional guidance for preparation and administration of study drug is provided in Section 9.4 and the study manual.

**Table 3-3 Schedule of Assessments for VX15-770-126 (Ivacaftor Arm: Study 124 Part A Only Subjects or Subjects Not From Study 124)**

Event/Assessment	Screening Period a	Treatment Period (Day 1 through Week 96)								ETT Visit b	Safety Follow-up Visit c	24-Week Follow-up OE

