### 5.2 Overview of Cystic Fibrosis in Infants and Young Children

The diagnosis of CF is suggested by the presence of 1 or more characteristic clinical features, a history of CF in a sibling, or a positive newborn screening test result, and is confirmed by laboratory evidence of abnormal CFTR protein function (a positive sweat test) and/or by genotyping analysis. Since the introduction and continued advances of newborn screening, many patients with CF are identified through a positive screen test and subsequently diagnosed within the first neonatal year. In the US, more than 80% of patients with CF are diagnosed by age 2. In the EU, approximately 60% of patients with CF are diagnosed by 1 year of age, and in the UK, approximately 83% of patients with CF are diagnosed by 1 year of age. Genotyping for mutations in the *CFTR* gene is now routine practice in many countries.

In infants with CF, pancreatic insufficiency and poor nutritional status are the most significant clinical manifestations of the disease. These factors often lead to poor growth with

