#### 8.2.1 Inclusion Criteria

1. Age <24 months at the Day 1 Visit
2. Confirmed diagnosis of CF, defined as a sweat chloride value  $\geq 60$  mmol/L by quantitative pilocarpine iontophoresis or 2 CF-causing mutations
  - If the results of the sweat chloride and/or the genotype test are documented in the subject's medical record, and the historic genotype result is approved by the Vertex medical monitor, the tests do not need to be performed at screening. A sweat chloride test must be performed if the sweat chloride value is not available in the subject's medical records and the value is needed to establish eligibility.
3. An ivacaftor-responsive *CFTR* mutation on at least 1 allele. Subjects will be eligible in countries/regions where ivacaftor is approved for use in subjects 2 years of age and older.
  - If a genotype test has been performed previously and is documented in the subject's medical record, the subject's eligibility must be approved by the Vertex medical monitor. If a historic genotype result is not available at screening or if the historic genotype result is not approved by the Vertex medical monitor, the subject will undergo *CFTR* genotype screening and the results must be reviewed before the first dose of ivacaftor. Subjects who have been enrolled and whose screening genotype does not confirm study eligibility will not receive study drug.
4. Hematology, serum chemistry, and vital signs results have no clinically significant abnormalities that would confound the study assessments, as judged by the investigator.
5. Weight at screening must be within the weight limits as defined for the study drug dose levels (Section 9.2.2) or according to the dosing guidelines identified in the "Justification for Dose Selection" memorandum effective at the time a subject is screened.
6. For subjects <3 months of age only, gestational age  $\geq 38$  weeks.
7. As judged by the investigator, parent or legal guardian must be able to understand protocol requirements, restrictions, and instructions; and must sign the ICF.

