## 9 STUDY IMPLEMENTATION

### 9.1 Overview of Study Design

[figure not shown]
This is a Phase 3, 2-arm, multicenter study.

Enrollment in Study 126 is closely linked to Study 124 which will enroll subjects according to defined age cohorts, starting with ages 12 to <24 months, followed sequentially by appropriately grouped descending age cohorts based on available PK data.

This study includes an ivacaftor arm (open-label, 96-week treatment period) and an observational arm. The study design is shown in Figure 9-1.

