### 9.2.3 Rationale for Study Assessments

The safety assessments are standard parameters for clinical studies in drug development. The scope of the assessments is considered appropriate for safety monitoring in the context of this study.

OEs are included in this study because a juvenile toxicity study conducted in albino rats to support clinical studies of ivacaftor in children <2 years of age demonstrated the presence of cataracts (lens opacities) when newborn rats were dosed with ivacaftor beginning at postnatal day (PND) 7 through PND 35, particularly at the highest dose tested. The results of chronic toxicity studies in the rat and dog did not reveal a cataractogenic potential. Although the relevance of this finding to humans is unknown, subjects will undergo an OE at the time points indicated in [Table 3-1](#), [Table 3-2](#), [Table 3-3](#), and [Table 3-4](#) to monitor the potential risk of cataracts (lens opacities).

The efficacy assessments were evaluated in Study 124 and are included in this study to evaluate the long-term effects of ivacaftor treatment. The efficacy assessments are widely accepted and are recognized as reliable, accurate, and relevant to the study of patients with CF.

Sweat chloride test: The sweat chloride test (quantitative pilocarpine iontophoresis) is a direct measure of CFTR activity in vivo and is the most commonly used diagnostic tool for CF. Sweat in normal individuals is hypotonic with respect to plasma chloride and sodium due to the absorption of chloride by CFTR and sodium by the epithelial sodium channel from sweat before the sweat reaches the surface of the skin. Because patients with CF have diminished CFTR activity, chloride ions are poorly reabsorbed, leading to elevated sweat chloride concentration. Sweat chloride can be measured in patients with CF of all ages, although levels do increase throughout the first 6 months of life.

Based on the mechanism of action of ivacaftor and the results of the previous Phase 3 studies of ivacaftor, the sweat chloride test is included in this study as a PD measure of the effect of ivacaftor on CFTR activity.

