### **11.4 Pharmacodynamics (Ivacaftor Arm Only)**

#### **11.4.1 Sweat Chloride**

Collection of sweat chloride samples will be performed at qualified study sites using an approved Macroduct® (Wescor, Logan, UT) collection device. Sweat chloride samples will be sent to a central laboratory for testing and interpretation of results. Individual sweat chloride test results will not be disclosed to the study sites. Specific instructions for the collection, handling,

processing, and shipping of sweat chloride samples to the central laboratory will be provided separately.

The sweat chloride test at the Day 1 Visit must be performed before the ivacaftor dose. Baseline sweat chloride test is not required at Day 1 if it was completed at screening. At subsequent visits through Week 24, the sweat chloride test must be performed within a window of  $\pm 2$  hours relative to the ivacaftor dose. After the Week 24 Visit, the sweat chloride test may be performed at any time during the visit. Change from baseline in sweat chloride will be analyzed as a secondary endpoint in this study.

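### Does the unrestricted use of a historical sweat chloride value as baseline (SAP 8.3.2) undermine the change-from-baseline summary?

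*SAP*

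**What the plan says.** SAP section 8.3.2 takes the mean of the two arms at a visit and subtracts the predose baseline. Samples under 15 µL and concentrations above 160 mmol/L are dropped, and one usable arm stands in for the mean. If the baseline test was not done, or both arms fail on volume, or both fail on concentration, "the most recent historical sweat chloride result may be used to impute the missing baseline value". Neither document qualifies that historical result further. The SAP Appendix B baseline window for ivacaftor-naïve children is study day 1 or earlier, with no lower bound. Under SAP section 8.1, missing data are otherwise left missing unless a rule is given.

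Three parts of the protocol bear on this:

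- Section 9.2.3 says sweat chloride can be measured at all ages, "although levels do increase throughout the first 6 months of life".
- Section 8.2.1 sets entry for children not from Study 124 Part B at "Age <24 months at the Day 1 Visit".
- Footnote p, in both Table 3-2 and Table 3-3, says of children with a value on record "for whom it is not needed to establish eligibility, the sweat chloride test at screening is not required". It then requires a predose Day 1 test unless the baseline test was done at screening. Section 11.4.1 agrees: "Baseline sweat chloride test is not required at Day 1 if it was completed at screening".

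**The concern.** Change in sweat chloride is the only secondary endpoint and there is no control arm, so each child's result depends entirely on that child's baseline. Protocol section 5.2 says that "many patients with CF are identified through a positive screen test and subsequently diagnosed within the first neonatal year", and a positive sweat test is one way to confirm the diagnosis. The latest result on file could therefore date from early infancy. Section 9.1 describes Study 124 cohorts "starting with ages 12 to <24 months, followed sequentially by appropriately grouped descending age cohorts based on available PK data", so first dosing can come much later than that test.

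A value taken while levels were still rising would sit below the true pre-dose level and hide part of the reduction at every visit. The word *may* adds a second worry. It does not say which eligible children get the historical value, and no count of them, and no summary without them, is planned. A reader of the change table could not tell how many baselines were historical or how old they were.

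**Working it through.** The plan states no power, effect size or SD for this endpoint, so there is no figure of its own to reproduce. The check covers four things: when the rule applies, which way it errs, how much it could move the summary, and what a restriction would gain.

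**1. When the rule applies.** For a child not from Study 124 Part B, the bias described needs all of the following:

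- no usable screening sample (footnote p allows the screening test to be skipped);
- a Day 1 predose test that was missed, or unusable in both arms;
- a most recent historical value from the first 6 months of life;
- a first dose materially later than that test.

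For rollover children the baseline is the Study 124 one (SAP section 8.1). How Study 124 handled missing values cannot be seen from these documents.

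**2. Direction.** Change = visit value − baseline. With assumed values of true baseline 100, historical value 90 and on-treatment value 50 mmol/L:

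- true change: 50 − 100 = −50;
- computed change: 50 − 90 = −40.

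The reduction is understated by exactly the 10 mmol/L shortfall, and by the same amount at every visit, so the pattern over time is preserved. The opposite error is also possible. Protocol section 8.2.1 begins its diagnostic criterion "Confirmed diagnosis of CF, defined as a sweat chloride value", with a threshold of at least 60 mmol/L. Selection on that threshold tends to favour high recorded values. The net direction across children is therefore not fixed.

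**3. Size.** Shift in mean change = k × d / n. Here k is the number of imputed children, d is the true pre-dose value minus the historical value, and n is the number with both a baseline and a value at that visit. The documents give neither k nor d, so both are assumed. With n = 75 (planned enrolment, SAP section 6.2):

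| k | d (mmol/L) | shift (mmol/L) |
|---|---|---|
| 0 | any | 0 |
| 1 | +10 | 1 × 10 / 75 = 0.13 |
| 4 | +10 | 4 × 10 / 75 = 0.53 |
| 8 | +20 | 8 × 20 / 75 = 2.13 |
| 8 | −10 | 8 × (−10) / 75 = −1.07 |

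Positive means the reduction is understated. Summaries are by visit and missing visits are not filled in, so the true n is likely to be below 75. If half the children contributed and all k were among them, each figure would double; for example, 4 × 10 / 37.5 = 1.07. These figures show how the effect scales. They are not an estimate of it.

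**4. What a restriction would gain.** A child tested in the first 6 months and first dosed at 12 to <24 months has a gap of at least 12 − 6 = 6 months and under 24 months. That is time, not error: the rise the protocol describes ends at 6 months, so a longer gap adds no further documented shortfall. A limit on the interval would miss the mechanism. A limit on age at test would address it, but the documents give no size from which to set one. Either limit would turn an affected child's change into a missing value at every visit. Nor is the mechanism special to imputation: a baseline properly measured before 6 months of age also precedes part of the natural rise.

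**The case for a change.** The best argument for a change is about discretion rather than bias. The study is open-label, the sponsor's own group does the analysis, and *may* does not fix who is imputed before on-treatment values are known. Protocol section 12.3.1 contains no historical fallback, and SAP section 2.1 does not list it as a modification. A stated rule, a count and a second table without imputed baselines would cost little.

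There is also a loose end. A child whose two baseline collections both followed the first dose is declared missing, yet the next paragraph of SAP 8.3.2 could be read to let a historical value in, as a test not performed at baseline.

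Much of this stands as description. The wording is permissive, no flag or count is specified, and the late-collection case can be read two ways. What does not follow is that the results would mislead. *Most recent* leaves no choice of which value to use, only whether to use one. Individual data, including derived variables, go into listings (Protocol section 12.3.1), so the values can be inspected even though no imputation flag is promised. A rule making the historical value mandatory could increase the use of early-infancy results. As for the laboratory, study samples go to a central one, but nothing in the documents shows that other laboratories read systematically differently.

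**Conclusion.** No change to the plan is needed. The gap is one of missing detail in a fallback rule that analysts can apply sensibly: use the latest pre-treatment value when the planned tests yield nothing usable, and note in the report where this was done. It is a fair trade-off between an imperfect baseline and losing the child from every change summary.

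For an affected child the error equals the full difference d. For the group mean it is k × d / n, which is zero if nobody is imputed and probably small otherwise, though neither k nor d can be derived from the documents. Observed sweat chloride by visit is unaffected, SAP section 8.3 restricts the analysis to descriptive statistics, and no test or error rate depends on it.

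The conclusion assumes that few baselines are historical. That is plausible given the required predose testing and the sufficiency of one usable arm, but it is not stated. If a large share were historical, the report would need to say so; at an assumed 15 of 75 with d = 20 the shift would be 15 × 20 / 75 = 4.0 mmol/L. That is a matter for reporting and does not require an amendment.
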